TITLE:

A Placebo-controlled, Double-blinded, Randomized Pilot Study of Bupivacaine Liposome Injectable Suspension (EXPAREL) for Minimally Invasive Supracervical Hysterectomies Postsurgical Analgesia

Unique Protocol ID: 2018-0-12

Document Date: December 12, 2019

Protocol Description

All patients who are scheduled for a robot-assisted or traditional laparascopic supracervical hysterectomy will be identified in the beginning of the week (Sunday) through the OR scheduler. All patients go to pre-admission testing, where they meet with a nursing staff who will coordinate their blood work and take a history. The co-investigators will be able to prescreen them in this fashion and on the day of the surgery confirm that they are eligible for the study.

After obtaining informed consent, participants will be assigned to the intervention or placebo group randomly. Randomization will be performed based computer-based random number generator (www.randomizer.org) which would generate two sets of random numbers containing 26 numbers from 1 to 52 with each number in a set remaining unique, which will be given to the pharmacy assistant director. The master list will be only accessible by pharmacy personnel. Hospital pharmacy staff will prepare the numbered package of either Exparel or normal saline (based on the randomization) in bubbled wrapped amber bag that will be given to the resident/attending who will proceed to inject the given medication during the prepping. Unlike normal saline which will be used as placebo, EXPAREL is milky in color, therefore to ensure adequate blinding of study investigators and surgeons an independent resident will unpack the package prior to the surgery and administer it to the patient in the absence of study investigators and surgeons during the prepping. All OB-GYN residents will be instructed about the proper injection procedure prior to the start of the study. All resident are equally capable, however senior residents (PGY3/PGY4) are assigned to do hysterectomies (a total of 12 residents). We expect performance bias but will rehearse with a model cervix in the simulation lab in order to diminish it. Only the pharmacy staff and independent residents will have access to the random generated list; all other staff including the investigators, surgeons, anesthesiologists, and nurses as well as patients will be kept blinded to the assigned treatments.

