Subjects in the intervention arm will receive paracervical block with 20 ml of extended-release liposomal bupivacaine (EXPAREL) at the 4 and 80'clock positions. Subjects in the placebo arm will receive paracervical/intracervical block with 20 ml of saline at the 4 and 8 o'clock positions. In both study arms the injection will be administered preoperatively.

Post operative pain management will be the same for both study groups. Immediately after surgery in the recovery room they will be able to receive ketorolac 30mgIV and/or acetominophen 1000mg IV, and if needed narcotics (as requested by the patient). This will all be recorded in the anesthesia record which is accessible to the co-investigators. Robot-assisted and traditional laparoscopic supracervical hysterectomy are ambulatory cases and we expect same day discharge. At home or in the hospital, all study participants will have oral acetaminophen 650mg q4-6 hr and NSAIDS 600mg q4-6 hours, as needed. If needed they will also have percocet 5-325mg q4-6 hours, the first dose of which will be recorded as the median time to narcotics.

Post operative pain management for both groups will include a combination of oral or parenteral nonsteroidal anti-inflammatory medications, and oral or parenteral opioids to be used as needed. Since most patients who undergo minimally invasive hysterectomy are discharged few hours after the surgery, data regarding the time, type and dose of postoperative analgesics used by the patient will be collected by providing the patient with a pain diary before discharge. Patient will be instructed to record use of any analgesics (including NSAIDS) for 72 hours whether the analgesic was prescribed by the surgeon or was taken at patient's own discretion. These data regarding the time, number and type of breakthrough analgesia will be used for evaluation of median time to first

break through opioid use and total opioid analgesic requirement.

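### The protocol describes time to first opioid in two conflicting ways, and neither brings in non-Percocet narcotics given in the recovery room

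*Protocol*

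**What the plan says.** All the relevant text is in the protocol under Protocol Description, in the two adjacent paragraphs on postoperative pain management and the short paragraph before them.

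- **Recovery room.** Patients may have ketorolac and acetaminophen "and if needed narcotics (as requested by the patient"). No agent is named. On documentation: "This will all be recorded in the anesthesia record which is accessible to the co-investigators".
- **Later regimen.** It opens with "At home or in the hospital, all study participants will have oral acetaminophen", adds an NSAID, and ends with "percocet 5-325mg q4-6 hours, the first dose of which will be recorded as the median time to narcotics".
- **Next paragraph, permitted opioids.** Both arms may have non-steroidal drugs "and oral or parenteral opioids to be used as needed".
- **Next paragraph, diary.** A pain diary is supplied before discharge. "Patient will be instructed to record use of any analgesics (including NSAIDS) for 72 hours", whether or not the surgeon prescribed the drug. These data are to yield the median time to a first breakthrough opioid and the total opioid requirement.
- **Timing of the block.** "In both study arms the injection will be administered preoperatively".
- **Size.** Randomization uses "two sets of random numbers containing 26 numbers from 1 to 52", that is, 26 per arm.

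**The concern.** Two paragraphs define the same quantity by different events and, in effect, from different sources. One event is the first dose of a named product. The other is the first breakthrough opioid of any kind, as the patient writes it down. Whoever builds the dataset has to choose, and the choice changes individual patients' times.

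The more serious problem is what both leave out. The protocol expects that some patients may ask for a narcotic immediately after surgery and allows parenteral opioids. Such a dose may be the patient's first postoperative opioid, yet neither description says that it enters the measure. The block is already in place at that point, so opioid use in the recovery room may itself be an effect of treatment. A measure labelled time to narcotics that passes over those doses cannot show such an effect.

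**Working it through.** The protocol states no rate, expected median or power for this measure, so there is no figure of its own to reproduce. The check sets the two descriptions side by side and then shows how far they could matter.

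**Step 1: what each description records.** The 0.5 h and 10 h below are assumed times.

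| Patient | Percocet wording | Diary wording | First opioid of any kind |
|---|---|---|---|
| Non-Percocet narcotic in recovery at 0.5 h, first Percocet at 10 h, no other opioid | 10 h | 10 h, if the diary starts after recovery | 0.5 h |
| Non-Percocet narcotic in recovery at 0.5 h, no opioid afterwards | no time | no time, on the same condition | 0.5 h |
| No narcotic in recovery, another opioid at home before Percocet | time of Percocet | time of the other opioid | time of the other opioid |
| Percocet in recovery at 0.5 h | 0.5 h | not clearly captured | 0.5 h |

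The third and fourth rows show that the descriptions conflict with each other. The first two show the gap they share.

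**Step 2: how many patients could be affected.** Assume recovery-room narcotic rates of 20% to 70%.

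- No recovery dose is Percocet: 52 × 0.20 = 10.4 and 52 × 0.70 = 36.4, so about 10 to 36 patients would get too late a time, or none, under the Percocet wording.
- Half are Percocet: 5.2 and 18.2, so about 5 to 18 patients.
- All are Percocet: none.

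**Step 3: when the arm median moves into the recovery room.** With 26 patients, the median lies between the 13th and 14th ordered times. If 14 or more of an arm receive a narcotic in recovery, the median time to any opioid falls within the recovery stay, whatever happens at home. The Percocet median can be hours later.

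**Step 4: illustration.** Assume first Percocet at 2 h plus an exponential time with median m, recovery doses uniform over 0 to 2 h and none of them Percocet, and no delay of Percocet after a recovery dose. The Percocet median is then 2 + m. For a recovery-room rate p, the any-opioid median is 2 + m·log2(2(1 − p)) if p ≤ 0.5, and 2 × 0.5/p if p > 0.5.

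| p, placebo/EXPAREL | m, placebo/EXPAREL | Percocet medians | Any-opioid medians |
|---|---|---|---|
| 50%/30% | 8 h/12 h | 10.0 vs 14.0 h | 2.0 vs 7.8 h |
| 50%/50% | 8 h/12 h | 10.0 vs 14.0 h | 2.0 vs 2.0 h |
| 70%/40% | 8 h/8 h | 10.0 vs 10.0 h | 1.4 vs 4.1 h |

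For example, 2 + 12 × log2(1.4) = 2 + 12 × 0.485 = 7.8 h. In the last row the benefit lies only in the recovery room, and the Percocet measure shows nothing. In the middle row it shows a difference that the any-opioid median does not. Simulated power for that middle row (26 per arm, two-sided Mann-Whitney at 5%, times capped at 72 h) is about 6% for any opioid and about 22% for Percocet, with simulation error of about 1 point.

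**The case against.** The strongest objection is that the Percocet sentence is not a working rule. A single patient's dose cannot be a median, so the sentence reads as shorthand for the outcome stated more carefully in the next paragraph, which covers any opioid. This stands in part. A reader might infer that the protocol commits itself to a Percocet-only event; it does not, because the second paragraph says otherwise. But that paragraph does not close the gap: the diary arrives before discharge, and nothing says that doses in the anesthesia record enter the time measure.

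A second objection is that breakthrough use could be meant to begin after the recovery room, a reasonable target for an extended-release block. The text does not exclude that intention, but it does not state it either. It sets no later clock start and does not set recovery doses aside. If that was the aim, the label time to narcotics is wrong and the wording still needs correcting.

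Third, Percocet may be given in hospital and could itself be the recovery-room narcotic. For those patients the Percocet wording gives the right time. The text permits other agents, however, so the definition cannot rest on this.

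Finally, harm to the arm comparison is not demonstrated. That stands in full: every rate and time in the illustration is assumed, and the any-opioid measure can be the weaker one. Nor does the protocol, as shown, name this measure as primary or tie the 52 patients to it.

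**Conclusion.** The point holds as an internal inconsistency with a shared gap. The two descriptions of time to first opioid conflict, and neither brings in non-Percocet narcotics given in the recovery room. That follows from the text alone and needs no assumption.

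The size does need assumptions. The protocol names neither the recovery-room agent nor how often it is used. The effect on the arm comparison therefore runs from none, if no non-Percocet narcotic is given there, to a large shift in the median if more than half of an arm receives one.

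Two stronger readings should be resisted. A reader might infer that the comparison is biased in a known direction; the illustration shows that the recorded difference can be too small or too large. A reader might also infer that recovery-room opioid data are lost; they are not, because the anesthesia record holds them and the co-investigators can see it. The fault is in the definition, not in data capture. Severity is minor to moderate.

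**What to change.** Reconcile the two paragraphs into one definition: time from end of surgery to the first postoperative opioid of any type or route, taken from the anesthesia or hospital record or the diary, whichever is earlier. Report time to first Percocet beside it under its own label, with no ranking of the two implied. Correct the wording so that each patient's time is what is recorded and the median is the group summary. As a clarification, state that the total opioid requirement draws on both sources. Censoring and opioid units can stay with the statistical analysis plan.

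The cost is about a sentence of protocol text and a little abstraction from a record already kept; the diary already asks for any analgesic. The drawback is that time to any opioid discriminates less when recovery-room use is common and similar in both arms, as in the assumed 50%/50% case. That is the reason to keep time to first Percocet. No change to treatment is proposed.

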The severity of pain will be assessed preoperatively in the holding area, at the time of PACU arrival, and at 12, 24, and 48 hours postoperatively using a numeric rating scale (NRS) from 0 to 10 with 10 being the worst pain the patient has ever experienced. The first two assessments will be performed in the hospital by the principal investigators and the remaining assessments will happen through a phone conversation with the patient after discharge from hospital. The NRS has been found to be a simple and valid alternative to the visual analog scale, and has been validated by Paice and Cohen in 1997. Based on this study which examined the validity of a verbally administered NRS using convergence methods, the correlation between the VAS and the NRS was strong and statistically significant ($\mathbf{r} = 0.847$, p < 0.001), supporting the validity of the verbally administered NRS. Type of pain (characterized as sharp, dull, stabbing, aching), location of pain (categorized as right upper quadrant, epigastric, left upper quadrant, right lumbar, umbilical, left lumbar, right iliac, hypogastric, left iliac) and radiation of pain will also be evaluated and recorded.

Based on the available evidence EXPAREL's adverse effects includes QT interval prolongation. The long QT prolongation syndrome usually does not manifest in any symptoms however one reported symptom is fainting, and if left persistent can lead to seizure activity and or death. To assess the incidence and severity of adverse events, patients' heart activity will be monitored during the surgery and any abnormal findings in the electrocardiogram pattern will be recorded. Additionally, before patient's discharge from hospital, the investigator will seek information on adverse event of the intervention by specific questioning and, as appropriate, by examination. Questions will include, do you feel faint and/or dizzy, do you have difficulty breathing. Information on all adverse events will be recorded immediately and the clinical course of each event will be followed until resolution, stabilization, or until it has been determined that the study treatment or participation is not the cause. Any adverse event that occurs after patient discharge and is considered to be possibly related to the study intervention will also be recorded. Adverse events can include readmission, signs and symptoms of infection, and bleeding.

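### The operation itself can redefine the top of the pain scale, which could bias the later NRS comparisons toward zero by an unknown amount

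*Protocol*

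**What the plan says.** The pain-assessment paragraph of the Protocol Description defines the numeric rating scale as running "from 0 to 10 with 10 being the worst pain the patient has ever experienced". The same scale is used in the holding area before surgery and then "at the time of PACU arrival, and at 12, 24, and 48 hours postoperatively using a numeric rating scale (NRS". The first two assessments are made in hospital. For the others, "the remaining assessments will happen through a phone conversation with the patient after discharge from hospital".

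Nothing in the paragraph says that the reference is the patient's worst pain *before* the operation, or that it must keep one meaning from one assessment to the next. The paragraph does not provide for recording each patient's earlier worst pain. In support of the scale it cites a correlation of r = 0.847 with a visual analog scale, "supporting the validity of the verbally administered NRS", but does not say which top anchor the cited study used.

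**The concern.** The top of the scale is the patient's own lifetime maximum, and pain from this operation can become that maximum. A patient whose postoperative pain exceeds anything before it should score 10 at that moment. Afterwards she has a higher reference, so the same later pain earns a lower number.

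This change of unit comes after randomisation and depends on early pain, which the block is meant to reduce. If the saline arm has more early pain, more of its patients would reset, and their scores at 12, 24 and 48 hours would be deflated relative to the EXPAREL arm. Randomisation does not protect against this, because the reset follows treatment. Analysis cannot reliably repair it either, since the earlier worst pain is not recorded and a peak between two assessments leaves no trace in the scores.

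**Working it through.** The document gives no effect size, standard deviation, power or sample-size calculation for the NRS, so there is no stated figure to reproduce. Its one relevant count is consistent: "two sets of random numbers containing 26 numbers from 1 to 52" gives 26 + 26 = 52. The check below tests the mechanism. **All pain levels in it are assumptions.**

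**Model.** Let W be the worst pain before surgery, P the peak surgical pain and x the current pain, all on one latent intensity scale.
- Anchor as written: score = 10 × x / max(W, P)
- Comparator, anchor fixed at the worst pain before surgery: score = 10 × x / W, capped at 10

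The two agree whenever P does not exceed W.

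**Worked example.** Assumed: P = 8 under placebo and 6 under active; at 24 h x = 4 and 3; later x = 3 in both.
- W = 8 (no reset). 24 h: 10 × 4/8 = 5.00 against 10 × 3/8 = 3.75, a difference of 1.25 with either anchor.
- W = 6 (the placebo patient resets to 8), 24 h. Fixed: 6.67 − 5.00 = 1.67. As written: 10 × 4/8 − 10 × 3/6 = 5.00 − 5.00 = 0.00.
- W = 6, later. Fixed: 5.00 − 5.00 = 0.00. As written: 10 × 3/8 − 10 × 3/6 = 3.75 − 5.00 = −1.25.

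So a reset can remove a true difference or create a false one, but only in patients whose surgical pain passes their earlier worst.

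**Arm level.** Simulation with 400,000 patients per arm; P has mean 7 (placebo) and 5 (active), SD 2; W has SD 2 and a mean of 12, 10, 8, 7 or 6, which sets the reset share. Later pain is a fraction of P, chosen to give latent arm differences of 1.2, 0.5 or 0.05. Entries are placebo minus active in NRS points, fixed anchor → anchor as written. Compare within a cell only, because the fixed-anchor value itself changes with W.

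| Reset share, placebo / active | Latent difference 1.2 | Latent difference 0.5 | Latent difference 0.05 |
|---|---|---|---|
| 4% / 1% | 1.03 → 1.00 | 0.43 → 0.41 | 0.04 → 0.02 |
| 14% / 4% | 1.24 → 1.11 | 0.52 → 0.41 | 0.05 → −0.03 |
| 36% / 15% | 1.51 → 1.10 | 0.65 → 0.28 | 0.07 → −0.21 |
| 50% / 24% | 1.65 → 1.02 | 0.74 → 0.16 | 0.10 → −0.36 |
| 64% / 36% | 1.72 → 0.90 | 0.82 → −0.01 | 0.13 → −0.54 |

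For the largest latent difference the loss is 0.03/1.03 = 3% in the first row, 0.13/1.24 = 10% in the second, 0.41/1.51 = 27% in the third and 0.82/1.72 = 48% in the last. The sign turns clearly negative only in the right-hand column, and there only from the third row down.

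**The case against.** The strongest reply is that a reset has a demanding precondition: surgical pain worse than any in the patient's life. The protocol describes ambulatory surgery with discharge expected the same day. It also states "Post operative pain management will be the same for both study groups", with intravenous ketorolac and/or acetaminophen in recovery, narcotics on request, and oral analgesics afterwards. This stands as a reason to doubt that resets are common. It does not exclude them, because the drugs are given as needed.

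Patients may also not rescale in the way the wording implies, and the spoken script is not shown. Both points stand and are part of why the size is unknown. Neither removes the problem in the definition, which is the only wording the document gives.

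The cited validation does not answer the point. A correlation between two scales says nothing about an anchor that moves between repeated assessments, and the anchor of that study is not stated.

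An imagined worst pain is subjective too, and may itself shift after severe pain. That stands. The proposed anchor closes the literal route by which this operation redefines the scale. It does not remove all variation between patients, which any self-reported anchor has and which randomisation balances in expectation.

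Finally, this is a pilot, and the document does not name the NRS as primary. The time to the first opioid for breakthrough pain and the total opioid requirement do not use the anchor. This stands and limits what is at stake.

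**Conclusion.** The concern holds as a conditional one. The anchor is personal, is not fixed in time, and can be moved after randomisation by pain that the treatment may affect. If resets are more frequent in the arm with more early pain, the NRS differences at 12, 24 and 48 hours can be biased toward zero. This rests on three assumptions that the document neither supports nor rules out: that a material share of patients exceed their earlier worst pain, that they rescale as the wording implies, and that the arms differ in early pain. With few resets the effect is negligible; with many it is material.

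Three stronger readings are tempting and are not supported.
- A reader might infer that the anchor *will* shrink or reverse the arm difference. The document gives no reset frequency, and a clear reversal appeared only with a sizeable reset share and a true later difference near zero.
- A reader might take a single pair of patients as the bias. With earlier worst pain 6, equal 24 h pain of 4 and peaks of 5 and 8, the scores are 4/6 × 10 = 6.67 and 4/8 × 10 = 5.00, a gap of 1.67. That is one chosen pair, not an arm-level figure. With an earlier worst pain of 8 or more, the gap is zero.
- A reader might infer that change from the preoperative score cannot be interpreted. The document plans no such analysis, a surgical reset cannot alter the preoperative score, and in patients who do not reset both scores share one scale.

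The point is worth acting on because the correction is nearly free, not because a large bias has been shown.

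**What to change.** In the pain-assessment paragraph, replace the top anchor with one that this operation does not redefine, for example *0 = no pain, 10 = worst pain imaginable*. State that the same wording is read out verbatim in the holding area, at PACU arrival and at each phone call.

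The cost is one wording change in the protocol and in the assessment script, with no added procedure, staff or patients. The downside is that any scores already collected under the present anchor must be flagged, since they may not be comparable with scores collected afterwards.

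### No ECG reading before the block is planned as study data, so old ECG abnormalities cannot be reliably told apart from new ones found during surgery

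*Protocol*

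**What the plan says.** All references are to the Protocol, under the unnumbered heading Protocol Description.

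- **Risk named (adverse-event paragraph).** "Based on the available evidence EXPAREL's adverse effects includes QT interval prolongation". The next sentence adds: "The long QT prolongation syndrome usually does not manifest in any symptoms". It goes on to mention fainting and, if the condition persists, seizure or death.
- **How it is observed (same paragraph).** To assess how often adverse events occur and how severe they are, "heart activity will be monitored during the surgery and any abnormal findings in the electrocardiogram pattern will be recorded".
- **When the block is given.** The randomization and blinding text has an independent resident unpack the product and "administer it to the patient in the absence of study investigators and surgeons during the prepping". The treatment paragraph says: "In both study arms the injection will be administered preoperatively".
- **What is collected beforehand.** At pre-admission testing, nursing staff "coordinate their blood work and take a history". The only pre-operative study measurement named is the pain score taken in the holding area.
- **Follow-up of events (adverse-event paragraph).** Each event is "followed until resolution, stabilization, or until it has been determined that the study treatment or participation is not the cause".

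**The concern.** The protocol singles out one cardiac risk and describes it as usually silent, so a measurement rather than a complaint is needed to detect it. The only ECG observation it plans comes after the exposure. Incidence refers to events that arise after treatment. A finding during surgery with no earlier reading shows that an abnormality is present, but not that it is new.

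At stake is how the ECG safety data read in a pilot of 52 patients. With 26 per arm, the list of ECG findings is likely to be short and to be read case by case. If a prolonged QT interval appears on the list, the first question will be whether the patient already had it.

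This belongs in the protocol because it concerns data collection. An analysis plan can say how to classify findings, but it cannot supply a reading that nobody noted.

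**Working it through.** The protocol gives no ECG rate, so there is no figure to reproduce. The check sets the statements against each other in time order.

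1. **Pre-admission testing.** Blood work and a history are named; an ECG is not. The text does not present these as a complete list, so a clinical ECG may exist for some patients. Nothing makes it study data.
2. **Holding area, day of surgery.** The pain score is taken. No cardiac reading is mentioned.
3. **Prepping.** The block, EXPAREL or saline, is injected. The protocol calls this preoperative in both arms.
4. **Surgery.** The heart is monitored and abnormal ECG findings are recorded.
5. **Recovery room.** Analgesics given there are "recorded in the anesthesia record which is accessible to the co-investigators". This is the only use the protocol makes of that record. It is not named as a source of a tracing from before the injection.
6. **Before discharge.** Patients are asked about faintness, dizziness and breathing, with examination as appropriate. These questions rely largely on symptoms, which the protocol says are usually absent in long QT.

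The first planned ECG observation (step 4) thus follows the exposure (step 3), and steps 1 and 2 plan nothing to compare it with. The history in step 1 may reveal known heart disease. By the protocol's own description of a usually symptomless condition, it is a weak substitute for a reading.

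**Effect on the comparison between arms.** Let *p* be the share of patients with a pre-existing abnormality, equal in expectation in both arms by randomization. Let *r_E* and *r_S* be the rates of new abnormalities under EXPAREL and saline. Suppose every old abnormality is seen and recorded, and old and new ones arise independently. Then:

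- recorded rate in an arm = *p* + (1 − *p*) × *r*
- difference between arms = (1 − *p*) × (*r_E* − *r_S*)

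If the two new-event rates are equal, the difference is zero, so old abnormalities do not create a spurious effect. If the rates differ, the recorded difference keeps its sign and shrinks by the factor (1 − *p*). The protocol gives none of *p*, *r_E* or *r_S*, so no number is put in.

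**Effect on a single patient.** Here randomization gives no help. Without an earlier reading, the planned data do not show which part of the recorded rate, *p* or (1 − *p*) × *r*, a given finding belongs to.

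**The case against.** The strongest reply is that recording is not counting. Capturing every abnormality and classifying it later is sound practice, and a new-or-worsened rule is commonly left to the analysis plan, which is not shown here. This stands. A reader might infer that the protocol will count old abnormalities as adverse events, or that it is at fault for having no such rule. The text supports neither. What survives is narrower: whatever rule is written later needs a pre-injection reading, and none is planned.

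Other replies stand in part:

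- **The saline arm already deals with this.** It does so for the group comparison. A reader might infer that the comparison between arms is biased in favor of one of them; it is not. The saline arm does not say whether one patient's abnormality is new.
- **Events are followed for cause.** The follow-up clause can end on resolution or stabilization as well as on a finding of no causal link, so it does not guarantee a causality ruling. It does not waive one either. It softens the point without supplying a baseline.
- **A baseline would not settle attribution.** Correct. A pre-injection reading excludes old abnormalities, but it cannot separate the block from surgery or anesthesia in one patient. That separation is the job of the saline arm.
- **The protocol never promises an incidence of QT prolongation.** Also correct. It speaks of adverse events in general, so there is no label to correct.
- **A pre-operative ECG may be done anyway.** Possibly. The document shows only that none is planned as study data, not that none is taken.

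**Conclusion.** The point holds as a cheap improvement to data collection. The protocol names a usually silent cardiac effect, looks for it only after the block has been given, and plans no earlier reading as study data. Pre-existing and new ECG abnormalities therefore cannot be reliably separated in the descriptive safety data.

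The reach is limited. The randomized comparison is not biased, and the analgesia results do not depend on it. The DSMB's regular review covers serious adverse events, so incidental ECG findings would rarely come before it.

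No magnitude is claimed. Any count of affected patients would rest wholly on assumed prevalences, and it would be an upper bound, since it would suppose that every old abnormality is seen, recorded and counted. The conclusion assumes only that the protocol's words preoperatively and during the surgery mean what they say about order, and that no pre-injection reading is collected as study data under a procedure not shown here.

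**What to change.** Add one sentence to the adverse-event paragraph. It should say that the surgical monitor is attached before the injection, and that the anesthesia staff then note the QT interval and any existing abnormality as study data. Keep recording every abnormal finding during surgery. Use the baseline note to mark each finding as pre-existing, new or worsened. The detailed classification rule can be left to the analysis plan.

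The cost is one extra note per patient. The protocol lists anesthesiologists among the blinded staff, and the note is made before the injection, so it cannot reveal or be influenced by the product given. The one practical condition is that the monitor is on before the injection, which the protocol does not state and the site should confirm. No separate or postoperative ECG is needed.

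### After discharge, adverse events are recorded only if thought possibly related, and adverse-event questioning is described only before discharge, so later incidence is likely to be understated

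*Protocol*

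**What the plan says.** All of the relevant text is in the Protocol, under Protocol Description.

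- **Aim.** The adverse-event paragraph opens with its purpose: "To assess the incidence and severity of adverse events". It ties this first to ECG monitoring during surgery.
- **Questioning.** Before the patient leaves hospital, "the investigator will seek information on adverse event of the intervention by specific questioning". The listed questions concern faintness or dizziness and difficulty breathing. No later adverse-event questioning is described.
- **General recording rule.** "Information on all adverse events will be recorded immediately", and each event is followed to resolution, stabilization, or "until it has been determined that the study treatment or participation is not the cause".
- **Rule after discharge.** "Any adverse event that occurs after patient discharge and is considered to be possibly related to the study intervention will also be recorded".
- **Examples.** "Adverse events can include readmission, signs and symptoms of infection, and bleeding".
- **Timing of discharge.** The postoperative pain management text treats these as ambulatory cases: "we expect same day discharge". It adds that most patients leave within a few hours of surgery.
- **Contacts after discharge.** Pain is scored at 12, 24 and 48 hours, and "the remaining assessments will happen through a phone conversation with the patient after discharge from hospital". A diary covers analgesic use for 72 hours. Neither is said to ask about adverse events.

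**The concern.** The general rule records an event first and settles its cause during follow-up. The rule for events after discharge reverses that order, making a judgement of possible relatedness the condition for entering the record at all. Because discharge is expected within hours of surgery, the narrower rule governs almost the whole postoperative period.

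That period is where the protocol's own examples belong. Readmission can occur only after discharge, and infection and bleeding can appear then. All three could readily be put down to the operation rather than the injection. A blinded investigator, not knowing whether drug or saline was given, has limited grounds for that judgement at the time.

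An event that was never written down cannot be reclassified later, and no statistical analysis plan can recover it. At stake is the completeness of the safety count in a small pilot whose stated aim includes incidence.

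**Working it through.** **Reading the text.** The protocol states no figure on this point, so there is none to reproduce. The question is whether the two recording sentences can both cover the period after discharge.

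1. Suppose the general sentence covers every event at any time. The next sentence, which adds post-discharge events that are possibly related, then adds nothing, and its condition does no work.
2. Suppose the general sentence covers events up to discharge. The next sentence then extends recording beyond discharge, limited to possibly related events. Both sentences have a purpose and they do not conflict.

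The second reading is the natural one. Under it, post-discharge events judged unrelated fall outside the rule, and recorded incidence is at or below true incidence.

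**What one missed participant is worth.** Input: two sets of 26 random numbers from 1 to 52 (randomization text), taken as 26 per arm and 52 in total.

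- Overall: 1/52 = 1.9 percentage points.
- Within an arm: 1/26 = 3.8 percentage points.
- Exact (Clopper-Pearson) two-sided 95% upper limit for 0/26: 1 − 0.025^(1/26) = 13.2%.
- The same limit for 1/26 solves (1 − p)^26 + 26p(1 − p)^25 = 0.025, giving p = 19.6%.

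**Illustration on assumed inputs.** The protocol gives neither a post-discharge event rate nor the share of events that would be judged unrelated. Both are assumed below, with one event per affected participant. Unrecorded participants = 52 × incidence × share judged unrelated. The points lost from overall incidence are in brackets.

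| Assumed incidence | 25% unrelated | 50% unrelated | 75% unrelated |
|---|---|---|---|
| 5% | 0.65 (1.25) | 1.3 (2.5) | 1.95 (3.75) |
| 10% | 1.3 (2.5) | 2.6 (5) | 3.9 (7.5) |
| 20% | 2.6 (5) | 5.2 (10) | 7.8 (15) |

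**Chance of seeing anything in an arm.** With true risk p and a fraction c of events recorded, the chance of at least one recorded event among 26 is 1 − (1 − pc)^26.

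- Assumed p = 10%: 93.5% with full recording, 73.6% with half.
- Assumed p = 5%: 73.6% with full recording, 48.2% with half.

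The table covers only the relatedness condition. Events missed because nobody asked would add to it.

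**The case against.** The strongest reply is that the text never forbids recording unrelated events. The general sentence has no time limit, and the later one adds to it rather than excluding anything. On that view the fault is unclear wording. This stands only in part: the wording does leave room for doubt, but the inclusive reading makes the relatedness condition pointless, and staff could reasonably apply the narrower one.

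A second reply is that the target is events of the intervention, as the questioning sentence puts it, so a relatedness condition fits. That sits poorly with an aim stated as the incidence of adverse events without qualification, and with readmission, infection and bleeding as the examples.

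Third, possible relatedness is a low bar, and blinded investigators might well call those examples possibly related. This is fair. It limits the likely loss and makes the 75% column look pessimistic, but it does not remove the condition or supply the missing questions.

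Fourth, the per-participant figures would hold for any missed event in any trial of this size, and the table rests on assumptions. Both points are correct. The numbers show how sensitive a pilot of 52 is to one omission; they do not estimate the loss.

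**Conclusion.** The concern holds, as an improvement to consider. The protocol sets a recording rule for the period after discharge that is narrower than its incidence aim, and describes adverse-event questioning only before an expected same-day discharge. Followed as written, post-discharge incidence is likely to be understated.

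The direction is clear if any later event is judged unrelated. The size cannot be derived: each omitted participant costs 1.9 points overall or 3.8 points in an arm, and the assumed ranges give about 0.7 to 7.8 of 52 participants (1.3 to 15 points). These figures assume 26 per arm and the natural reading of the two sentences.

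Two things are not claimed. No bias between arms is shown, since investigators and patients are stated to be blinded. No effect on the Data Safety and Monitoring Board's counts is claimed either: its assessment of serious events carries no relatedness condition, and how reports reach it is not described.

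**What to change.** Ask the same scripted adverse-event questions at the existing 12, 24 and 48 hour calls in both arms: faintness or dizziness, difficulty breathing, readmission, signs of infection, bleeding. Replace the post-discharge sentence with wording such as:

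> All adverse events that come to the investigators' attention up to and including the 48-hour call will be recorded regardless of suspected relationship; relationship will be recorded as a separate item by a blinded investigator. Any serious adverse event, including readmission, that comes to the investigators' attention later during the study will also be recorded regardless of relationship. Later non-serious adverse events considered possibly related to the study intervention will also be recorded.

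The present condition then applies only to later non-serious events. The cost is slightly longer calls and a longer listing with more unrelated events; no visit or procedure is added. The 48-hour limit follows the last scheduled call, so non-serious events after it that are judged unrelated, including late minor infection or bleeding, would still go unrecorded, as now.
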